10.2. Safety analysis

Data name	Derivation and calculation methods
	The adverse events for analysis should include not only the events derived
	from the survey form but also the events covered in the detailed
	investigation which has been described by the physicians at a contracted
	site/department even though not derived from the survey form in "AE
	matching results".
Adverse event	With adverse event: at least 1 record on adverse event(s) exists
	Without adverse event: other than the above.
	When adverse events are counted per SOC, the identical SOC in a patient
	should be counted as 1 whereas the same PT in the same patient be
	counted as 1 for PT. When no applicable patients were observed, display
	"0" for the number of patients and "0.00" for the percentage.
	Based on the seriousness criteria for company assessment which are
	provided in "AE matching results", regard the events which have been
	assessed to be serious as serious adverse events.
Seriousness of	With serious adverse event: at least 1 record on serious adverse event(s)
adverse events	exists
	Without serious adverse event: other than the above.
	Follow the way of counting adverse events to count serious adverse
	events.
	All events which are not determined as "Not related" based on the
	company's causality assessment provided in "AE matching results" are
Adverse reaction	regarded as an adverse reaction.
	With adverse reaction: at least 1 record on adverse reaction(s) exists
	Without adverse reaction: other than the above.

Data name	Derivation and calculation methods
	Follow the way of counting adverse events to count adverse reactions.
	Based on the seriousness criteria for company assessment which are
	provided in "AE matching results", regard the events which have been
	assessed to be serious as serious adverse reactions.
Serious adverse	With serious adverse reaction: at least 1 record on serious adverse
reactions	reaction(s) exists
	Without serious adverse reaction: other than the above.
	Follow the way of counting adverse events to count serious adverse
	reactions.
	If more than one identical SOC or PT are found in a patient in counting
	adverse events, adverse reactions, serious adverse events, and serious
	adverse reactions per outcome, identify the events to be counted with the
Outcome	following priority, using the outcomes for company assessment provided
	in "AE matching results".
	[1] death [2] with sequela [3] not recovered [4] unknown [5] not provided
	[6] recovering [7] recovered
Death case	At least a piece of data on "death" is found as the outcome of the adverse
Death case	events during the safety analysis period.
	Use the onset date for company assessment provided in "AE matching
	results".
	When the first administration date of Humira and the adverse-event onset
	date can be identified as the complete date, they can be used for
Days from the first	calculation.
administration date of	When the first administration date of Humira <= the adverse-event onset
Humira to the	date
adverse-event onset	Adverse-event onset date - the first administration date of Humira + 1
date	When the first administration date of Humira > the adverse-event onset
	date
	Adverse-event onset date - the first administration date of Humira
	When more than one identical PT is found in a patient, use the first onset
	date to identify the adverse event to be counted.
Days from the	Use the onset date and the outcome confirmation date (recovered or
adverse-event onset	recovering)for company assessment provided in "AE matching results".
date to the outcome	When the adverse-event onset date and the outcome confirmation date can
confirmation date	be identified as the complete date, they can be used for calculation.
(recovered or	Outcome confirmation date - adverse-event onset date + 1

Data name	Derivation and calculation methods
recovering)	When more than one identical PT is found in a patient, choose the event which persisted longest until the recovery or the outcome confirmation date.
Incidence of adverse reactions, incidence of serious adverse reactions, incidence of adverse events, incidence of serious adverse events	Calculate the incidence of adverse reactions, incidence of serious adverse reactions, incidence of adverse events, incidence of serious adverse events with the number of patients with any of the reactions/events in numerator and the number of patients in the safety analysis group in denominator. Provide how to calculate in each table at Chapter 13 and thereafter if other calculation methods are used.

10.3. Effectiveness analysis

Data name	Derivation and calculation methods
General improvement	Use what has been provided in "general improvement rate (primary
rate	physician's assessment" of the survey form.
	Partial Mayo score + endoscopic finding score
Mayo score	* Only the survey forms with all the scores assessed are calculated (if any
	unassessed scores are included, they are excluded from calculation)
Remission of Mayo	It should be calculated as 1 or less if the Mayo score is 2 or below and a
score	sub-score.
	Stool frequency score, rectal bleeding score and physician's global
Dontiel Mayo goons	assessment
Partial Mayo score	* Only the survey forms with all the scores assessed are calculated (if any
	unassessed scores are included, they are excluded from calculation)
Remission of partial	It should be calculated as 1 or less if the partial Mayo score is 2 or below
Mayo score	and a sub-score.
	Partial Mayo score at every assessment decreases by 2 points or more and
	by 30% or more in comparison to the partial Mayo score when
Improvement of	administration was started. In addition, at least one of the following
partial Mayo score	conditions shall be met.
(responder)	•Rectal bleeding score has been decreased by at least 1 point since the
	administration was started.
	• Rectal bleeding score is ≤1.
Endoscopy results	Use what has been provided in "endoscopic findings" of the survey form.

11. How to stratify data

Data	How to stratify
Dosage and	160mg→80mg→40mg once every two weeks and no changes thereafter,
administration	other
	The first administration to <week (1-28="" 4="" administration,="" days)<="" of="" td=""></week>
	≥Week 4 of administration and <week (29-56="" 8="" administration="" days)<="" of="" td=""></week>
	≥Week 8 of administration and <week (57-168="" 24="" administration="" days)<="" of="" td=""></week>
	≥Week 24 of administration and <week (169-336<="" 48="" administration="" of="" td=""></week>
Dose period	days)
	≥Week 48 of administration and ≤Week 52 of administration (337-365
	days)
	Unknown
	* when the first administration is counted as 1.
	≥1 and ≤4,
D	≥5 and ≤12,
Dosing frequency	≥13 and ≤24,
	≥25
	≥40mg and ≤500mg,
Total dose	≥501mg and ≤1000mg,
	≥1001mg
Reason for	Development of adverse event, lack of effectiveness, patient's wish, no
discontinuation	visit, others, multiple answers are acceptable
Reason for	Treatment/surgery, pregnancy, concern about the onset of adverse events,
discontinuation, other	the condition improved, the condition worsened
reasons	Poor adherence, for study
Sex	Man, women, unknown/not provided
Pregnancy/nursing	Not pregnant/nursing, pregnant, nursing, unknown/not provided
Race	Japanese, other Asians, others, unknown/not provided
Age (in years)	$<15, \ge 15$ and $<65, \ge 65$, unknown/not provided
	<30, ≥30 and <40, ≥40 and <50, ≥50 and <60, ≥60, unknown/not
Body weight (kg)	provided
BMI(kg/m ²)	$<18.5, \ge 18.5 \text{ and } <25, \ge 25 \text{ and } <30, \ge 30, \text{ unknown}$
Duration of illness (in	
years)	$<2, \ge 2$ and $<10, \ge 10$, unknown/not provided
Indication (registration	Colitis ulcerative, others, not provided
form)	

Data	How to stratify
Allergy history	Without the history, with the history, unknown/not provided
Smoking history	Without the history, with the history, unknown/not provided
Detailed classification of smoking history	Smoking, only in the past (not smoking now), unknown
Tuberculosis test	Not conducted, conducted
Hepatitis B test	Not conducted, conducted
Complications	Without the history, with the history, unknown/not provided
Detailed classification of complications	Liver disorder, renal disorder, blood disorder, respiratory disorder, others
Other classification of complications	Diabetes mellitus, osteoporosis, malignant tumour, others
Medical history	Without the history, with the history, unknown/not provided
Detailed classification of medical history	Tuberculosis, non-tuberculous mycobacteriosis, interstitial pneumonia, bronchitis bacterial, aplastic anaemia, pancytopenia, malignant tumour, others
Prior medications for colitis ulcerative	Without the history, with the history, unknown/not provided
Details classification of	Infliximab, other biological products, aminosalicylic acid products,
prior medications for	corticosteroid, azathioprine & 6-mercaptopurine, tacrolimus &
colitis ulcerative	ciclosporin, antibiotics, prior medication: others
Prior treatment for colitis ulcerative	Without the history, with the history, unknown/not provided
Details classification of prior treatment for colitis ulcerative	Leukocytapheresis, surgery, enteral nutrition therapy, intravenous nutrition therapy, others
Treatment history with biological products	Without the history, with the history, unknown/not provided
Detailed classification of "with" biological products	Infliximab, other biological products Reason for discontinuation: lack of effectiveness Reason for discontinuation: adverse events Reason for discontinuation: others Reason for discontinuation: unknown/not provided
Concomitant medications for colitis ulcerative Details classification of	Without the history, with the history, unknown/not provided
Details classification of	Aminosalicylic acid products, corticosteroid, azathioprine &

Data	How to stratify
concomitant	6-mercaptopurine, tacrolimus & ciclosporin, antibiotics, others
medications for colitis	
ulcerative	
Concomitant therapy	Without the history, with the history, unknown/not provided
for colitis ulcerative	without the history, with the history, unknown/hot provided
Details classification of	Leukocytapheresis, surgery, enteral nutrition therapy, intravenous
concomitant therapy for	nutrition therapy, others
colitis ulcerative	nutrition dicrapy, outers
Site of disease	Rectum, colon, unknown/not provided
Details classification of	
a site of disease	Sigmoid, descending, transverse, ascending
"colon"	
Site of disease by type	Rectal only (no colon), including any of transverse or ascending site,
Site of disease by type	others, unknown/not provided
Self administration	Without the history, with the history, unknown/not provided
Self-administration	Without the history, with the history, unknown/not provided
error	without the history, with the history, unknown/hot provided
General improvement	Effective or better, ineffective
rate	Effective of better, memective
Detailed classification	
of effective or better of	Markedly effective, effective
general improvement	iviairodiy ciicciive, ciicciive
rate	
Partial Mayo score	\geq 0 and \leq 3, \geq 3 and \leq 6, \geq 6 and \leq 9, unknown/not provided
CRP	$<0.3 mg/dL, \ge 0.3 mg/dL$ and $<1 mg/dL, \ge 1 mg/dL$, unknown/not provided
Endoscopy results	normal or remission mucosa, mild, moderate, severe

12. Handling of data for test/assessment periods

12.1. Assessment period for the administration status of Humira

Time allowance of assessment period with the first administration date of Humira as 1 is as follows:

Assessment period	Time Allowance(Day)	
The first administration to <week 4="" of<="" td="">1~28	</week>	1~28	
administration	1~28	
≥Week 4 of administration and <week 8="" of<="" td="">29~56	</week>	29~56	
administration	29~30	
≥Week 8 of administration and <week 24="" of<="" td="">57~168	</week>	57~168	
administration	3/~108	
≥Week 24 of administration and <week 48="" of<="" td="">169~336	</week>	169~336	
administration	109~330	
≥Week 48 of administration and ≤Week 52 of	337~365	
administration	33/~303	

12.2. Assessment period for the onset status of adverse reactions

Time allowance of assessment period with the first administration date of Humira as 1 is as follows:

Assessment period	Time Allowance(Day)	
The first administration to <week 4="" of<="" td="">1-28	</week>	1-28	
administration		
≥Week 4 of administration and <week 8="" of<="" td="">29-56	</week>	29-56	
administration	29-30	
≥Week 8 of administration and <week 24="" of<="" td="">57-168	</week>	57-168	
administration	37-168	
≥Week 24 of administration and <week 48="" of<="" td="">169-336	</week>	169-336	
administration	109-330	
≥Week 48 of administration and ≤Week 52 of	337-365	
administration	337-303	
> Week 52 of administration	366-	

12.3. Assessment period for Mayo score

Time allowance of assessment period with the first administration date of Humira as 1 is as follows:

Assessment period	Time Allowance(Day)
At the first administration	-14 ~ 1 (scheduled date: 1)
Week 24 of administration	155 ~ 183 (scheduled date: 169)
Week 52 of administration	337 ~ 393 (scheduled date: 365)
A4 diamandian	The final administration date of Humira + 14 (scheduled date:
At discontinuation	the final administration date of Humira)
At final assessment	Data for the final assessment period among the assessment
At imai assessment	applicable to the Time Allowance of each assessment period.

The data for analysis should derive from the one the closest to the scheduled date within Time Allowance. If there are more than one data dated on the same day, select the higher value.

12.4. Assessment period for partial Mayo score

Time allowance of assessment period with the first administration date of Humira as 1 is as follows:

Assessment period	Time Allowance(Day)
At the first administration	-14 ~ 1 (scheduled date: 1)
Week 4 of administration	15 to 42 (scheduled date: 29)
Week 8 of administration	43 to 70 (scheduled date: 57)
Week 16 of administration	98 to 126 (scheduled date: 112)
Week 24 of administration	155 ~ 183 (scheduled date: 169)
Week 52 of administration	337 ~ 393 (scheduled date: 365)
At discontinuation	The final administration date of Humira + 14 (scheduled date:
	the final administration date of Humira)
At final assessment	Data for the final assessment period among the assessment
	applicable to the Time Allowance of each assessment period.

The data for analysis should derive from the one the closest to the scheduled date within Time Allowance. If there are more than one data dated on the same day, select the higher value.

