	Data credibility cannot be confirmed: inconsistency was found in the
	survey form
Patients in the safety	The remaining patients after the patients excluded from the safety
analysis group analysis group are removed from the patients whose survey fo	
	locked
Patients excluded from	The patients who satisfy the exclusion criteria for the effectiveness
the effectiveness analysis	analysis group. See Reference Data "Inclusion/exclusion of patients" for

Name of group	Definition	
group	the exclusion criteria for the effectiveness analysis group.	
	The exclusion items are as follows:	
	Breach of registration criteria: Not the disease to be surveyed	
	Effectiveness is not assessable	
Patients in the	The remaining patients after those excluded from the effectiveness	
effectiveness analysis	analysis group are removed from the patients in the safety analysis	
group	group.	

9. General agreement items for analysis

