9.1. Handling of missing data

No missing data at any time are imputed for analysis. Note that entry data need to be imputed in some items and the imputation method for imputation-required items is defined in the definitions of each item at Chapter 10 or thereafter.

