12.6. Assessment period for CRP

Time allowance of assessment period with the first administration date of Humira as 1 is as follows:

Assessment period	Time Allowance(Day)
At the first administration	-14 ~ 1 (scheduled date: 1)
Week 4 of administration	15 to 42 (scheduled date: 29)
Week 8 of administration	43 to 70 (scheduled date: 57)
Week 24 of administration	155 ~ 183 (scheduled date: 169)
Week 52 of administration	337 ~ 393 (scheduled date: 365)
At discontinuation	The final administration date of Humira + 14 (scheduled date:
	the final administration date of Humira)
At final assessment	Data for the final assessment period among the assessment
At final assessment	applicable to the Time Allowance of each assessment period.

The data for analysis should derive from the one the closest to the scheduled date within Time Allowance. If there are more than one data dated on the same day, select the higher value.

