Calculate the number of target patients, the mean and standard deviation of partial Mayo score, the mean and standard deviation of changes in partial Mayo score for each assessment period, and conduct a paired-t test which compares the values at the initial administration.

In addition, calculate the mean of the mean days to the final assessment and the standard deviation.

Note: Follow "12.4 Assessment period for partial Mayo score" for Time Allowance of assessment period.

The analysis covers only the patients with the assessment applicable to Time Allowance of the first administration and each assessment period.

Multiplicity in the test will be adjusted by the Bonferroni method.

"3.1.5.1 Changes in the remission rate at each point of partial Mayo Score (Observed Case)"

Patients for analysis: patients in the effectiveness analysis group

Analysis objective: to show the remission rate of partial Mayo score per assessment period.

Analysis item: calculate the number of patients in the analysis groups.

Calculate the number of target patients, the percentage to the number of patients who achieved a remission and the number of target patients, 95%CI of the remission rate, and conduct a McNemar test for the first administration per assessment period.

In addition, prepare a line plot to describe the percentage to the target patients among the patients who achieved a remission per assessment period.

X-axis: assessment period (in week)

Y-axis: remission rate (%)

Note: Follow "12.4 Assessment period for partial Mayo score" for Time Allowance of assessment period.

The analysis covers only the patients with the assessment applicable to Time Allowance of the first administration and each assessment period.

For the confidence interval, use the Clopper-Pearson's confidence interval.

Refer to "10.3 Effectiveness analysis" for the calculation method and remission rate.

"3.1.5.2 Changes in the remission rate (NRI) at each point of partial Mayo Score"

Patients for analysis: patients in the effectiveness analysis group

Analysis objective: to show the remission rate of partial Mayo score per assessment period.

Analysis item: calculate the number of patients in the analysis groups.

Calculate the number of target patients, the percentage to the number of patients who achieved a remission and the number of target patients, 95%CI of the remission rate, and conduct a McNemar test for the first administration per assessment period.

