In addition, prepare a line plot to describe the percentage to the target patients among the patients who achieved a remission per assessment period.

X-axis: assessment period (in week)

Y-axis: remission rate (%)

Note: Follow "12.4 Assessment period for partial Mayo score" for Time Allowance of assessment period.

The analysis covers only the patients with the assessment applicable to Time Allowance of the first administration and each assessment period.

For the confidence interval, use the Clopper-Pearson's confidence interval.

Refer to "10.3 Effectiveness analysis" for the calculation method and remission rate.

NRI: when it is unknown whether the remission is achieved, impute the data without remission.

"3.1.7.1 Remission rate at Week 52 in patients who achieved a remission at Week 8 of administration based on partial Mayo score"

Patients for analysis: Patients in the effectiveness analysis group (the patients who did not achieve a remission when the administration was started but achieved the remission at Week 8 of administration in partial Mayo score)

Analysis objective: to show the remission rate of partial Mayo score at Week 52 of administration in patients in the analysis group.

Analysis items: calculate the number of target patients, the percentage to the number of patients who achieved a remission at Week 52 of administration and the target patients, and the confidence interval of the remission rate. (calculate them in both Observed Case and NRI patterns)

Note: the patients for analysis should have partial Mayo score at the first administration and Week 8 of administration and achieved a remission at Week 8 of administration except those who had already achieved a remission in partial Mayo score at the first administration.

Follow "12.4 Assessment period for partial Mayo score" for Time Allowance of assessment period.

For the confidence interval, use the Clopper-Pearson's confidence interval.

"3.1.7.2 Remission rate at Week 52 in patients who achieved the response as an index of partial Mayo score at Week 8 of administration"

Patients for analysis: Patients in the effectiveness analysis group (the patients who achieved a response at Week 8 of administration in partial Mayo score)

Analysis objective: to show the remission rate of partial Mayo score at Week 52 of administration in patients in the analysis group.

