Note: the patient background factors are as follows:

Age (year), the elderly, pediatrics, sex, body weight (kg), BMI (kg/m²), duration of illness (year), complications, complication: hepatic function disorder, complication; renal impairment, complication: blood disorder, complication: respiratory disorder, complication: diabetes mellitus, complication: osteoporosis, complication: malignant tumour, medical history; medical history: tuberculosis, medical history: non-tuberculous mycobacteriosis, medical history: interstitial pneumonia, medical history: bronchitis bacterial, medical history: aplastic anaemia, medical history: pancytopenia, medical history: malignant tumour, allergy history, smoking history, detailed history of smoking history, the administration status of Humira: self-administration, prior medication, prior medication: biological product, prior medication Infliximab, prior medication: other biological product, prior medication: aminosalicylic acid drug, prior medication: corticosteroids, prior medication: azathioprine, prior medication 6-mercaptopurine, prior medication: azathioprine & 6-mercaptopurine, prior medication: tacrolimus & ciclosporin, prior treatment, prior treatment: leukocytapheresis, prior treatment: surgery, prior treatment: enteral nutrition therapy, prior treatment: intravenous nutrition therapy, concomitant medication, concomitant medication: aminosalicylic acid drug, concomitant medication: corticosteroids, concomitant medication: azathioprine, concomitant medication: 6-mercaptopurine, concomitant medication: azathioprine & 6-mercaptopurine, concomitant medication: tacrolimus & ciclosporin, concomitant treatment, concomitant treatment: leukocytapheresis, concomitant treatment: surgery, concomitant treatment: intravenous nutrition therapy, concomitant treatment: enteral nutrition therapy, site of disease by type, partial Mayo score, CRP

"3.4.1 Aggregation for effectiveness per patient background factor (partial Mayo score)" Patients for analysis: patients in the effectiveness analysis group

Analysis objective: to show the remission of partial Mayo score at the final assessment as the primary endpoint per patient background factor and analyze them.

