Analysis items: calculate the number of all patients, the percentage to the number of patients who achieved a remission in partial Mayo score and all patients, the number of patients who failed to achieve a remission in partial Mayo score and the percentage to number of all patients, the tests for remission (Fisher's exact test for nominal-scale factors and Man-Whitney's u test for ordinal-scale factors) per the following patient background factor:

Note: Refer to "3.4 Aggregation for effectiveness per patient background factor (general improvement rate)" for patient background factors.

"3.5 Changes in CPR level"

Patients for analysis: patients in the effectiveness analysis group

Analysis objective: to show measured CPR levels at each assessment period.

Analysis items: calculate CRP's summary statistics (number of cases, mean, standard deviation, minimum value, 1st quartile value, the median, 3rd quartile value and the maximum value) per assessment period.

Note: Follow "12.6 Assessment period for CRP" for Time Allowance of assessment period.

The analysis covers only the patients with the assessment applicable to Time Allowance of the first administration and each assessment period.

"3.6 The status of corticosteroid use and the remission in partial Mayo score in patients who used corticosteroids when administration was started (Observed Case)"

Patients for analysis: patients in the effectiveness analysis group

Analysis objective: to show the status of corticosteroid use and with/without remission in partial Mayo score per assessment period in patients who concomitantly used corticosteroids when administration was started

Analysis items: calculate the number of target patients, the percentage to the number of patients with/without concomitant use of corticosteroids and to the number of target patients, and the percentage to the number of patients who achieved/failed to achieve a remission in partial Mayo score and to the number of target patients.

Note: The target patients to be counted in each assessment period shall receive Humira in each Time Allowance defined in "12.4 Assessment period of partial Mayo score".

The target patients who concomitantly used corticosteroids at each assessment period shall receive corticosteroids at each scheduled date defined in "12.4 Assessment period of partial Mayo score".

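### As written, the SAP's final-assessment rule lets a pre-treatment score or CRP stand as the final value when no later in-window value exists

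*SAP*

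**What the plan says.** **The rule.** The final-assessment row in SAP 12.4 (partial Mayo score) selects the last data "applicable to the Time Allowance of each assessment period". Sections 12.3 (Mayo score) and 12.6 (CRP) use the same rule. In all three tables the first row in the assessment-period column is first administration, with a window of Day -14 to Day 1.

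**Where it is used.**
- Table 3.4.1 aims "to show the remission of partial Mayo score at the final assessment as the primary endpoint per patient background factor". It carries no note requiring a score after first administration. Table 3.4 gives the same primary-endpoint label to the physician's general improvement rating, which does not use this rule.
- Tables 3.1.1 and 3.1.4 (change in Mayo and partial Mayo score, both labelled Observed Case) and Table 3.5 (CRP) carry this restriction: "The analysis covers only the patients with the assessment applicable to Time Allowance of the first administration and each assessment period".

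**Related provisions.**
- SAP 9.1: "No missing data at any time are imputed for analysis". It allows exceptions that are defined item by item from chapter 10 onward.
- SAP section 8 removes patients from the effectiveness group under "Effectiveness is not assessable", with the criteria held in separate reference data.
- Table 3.1.7.1 takes Week 8 remitters "except those who had already achieved a remission in partial Mayo score at the first administration", so the plan foresees patients in remission at baseline.

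**The concern.** First administration is listed as an assessment period, and the final value is drawn from all listed periods. A programmer who follows the text will therefore give a baseline-only patient the baseline value as the final result. That is baseline carried forward, although it is not declared as imputation. It sits badly with the general principle in 9.1 and with the Observed Case labels.

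At stake are the final-assessment rows of the change tables and their paired t-tests, the final CRP summary, and the outcome in the Table 3.4.1 factor analysis. Factors affecting effectiveness are a stated objective of the survey.

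**Working it through.** **1. The rule applied to example patients.** The scheduled windows in SAP 12.4 are Day -14 to 1, 15-42, 43-70, 98-126, 155-183 and 337-393. All the example patients continue treatment, so the discontinuation row does not apply.

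| Partial Mayo scores recorded | Final value as written | Change | Final value, post-baseline windows only |
|---|---|---|---|
| Day 1: 7 | 7 (Day 1) | 0 | none |
| Day 1: 7; Day 10: 5 | 7 (Day 1) | 0 | none |
| Day 1: 7; Day 85: 1 | 7 (Day 1) | 0 | none |
| Day 1: 7; Day 225: 1 | 7 (Day 1) | 0 | none |
| Day 1: 7; Day 57: 2 | 2 (Day 57) | -5 | 2 (Day 57) |

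The restriction in Tables 3.1.1, 3.1.4 and 3.5 does not remove the first four patients, because one baseline value fills both roles.

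**2. Can such patients occur?** Days 2-14, 71-97, 127-154 and 184-336 lie in no scheduled partial Mayo window: 13 + 27 + 28 + 153 = 221 of the 364 days from Day 2 to Day 365. Protocol section 8(3) collects the score at week 32. That is Day 32 × 7 + 1 = 225, inside the last gap. This shows that the case is possible. It does not measure how often it occurs.

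**3. Effect on mean change.** Let f be the baseline-only share of patients in the final row, and D the mean change in the others.

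Reported mean change = (1 - f) × D + f × 0 = (1 - f) × D.

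The documents do not give f. For assumed values of 2%, 5%, 10% and 20%, the factor is 0.98, 0.95, 0.90 and 0.80.

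**4. Effect on remission in Table 3.4.1.** Let r be remission among patients with a post-baseline value, and p0 the baseline remission rate among baseline-only patients.

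- Rule as written: (1 - f) × r + f × p0
- Explicit non-responder imputation (NRI): (1 - f) × r
- Patients without a post-baseline value excluded: r

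For illustration r = 30%, the planning rate. Both f and p0 are assumptions.

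| f | Excluded | As written, p0 = 0 | As written, p0 = 5% | Explicit NRI |
|---|---|---|---|---|
| 2% | 30.0 | 29.4 | 29.5 | 29.4 |
| 5% | 30.0 | 28.5 | 28.75 | 28.5 |
| 10% | 30.0 | 27.0 | 27.5 | 27.0 |
| 20% | 30.0 | 24.0 | 25.0 | 24.0 |

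With p0 = 0 the rule as written equals NRI. What it adds beyond NRI is f × p0: 0.1, 0.25, 0.5 and 1.0 percentage points at p0 = 5%.

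**5. What the plan's 30% unscored figure is.** The sample-size calculation reproduces: 1500 × 0.30 = 450 remaining at Week 52, and 450 × 0.70 = 315 with a Mayo score. The half-width is 1.96 × √(0.3 × 0.7 / 315) = 5.06%, which the plan gives as ±5.1%. The 30% is thus the share without a Mayo score among patients still present at Week 52. It is not the share with a baseline value and nothing later, and it cannot serve as f.

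**The case against.** **Intent.** The strongest reply is that the SAP's own usage points to post-baseline periods. Section 13.3 repeatedly names first administration and each assessment period as two things, which would be redundant if the second included the first. A change from the initial value, tested per period, also has no meaning for the baseline row. This is a fair reading of what was meant. It does not settle what will be programmed: the tables in 12.3, 12.4 and 12.6 list first administration as an assessment period, and Table 3.4.1 lacks the note altogether.

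**Analysis set.** Patients whose effectiveness is not assessable are excluded, and those criteria cannot be seen here. They may remove some baseline-only patients. No visible text makes a post-dose Mayo score or CRP a condition, so a patient with a general improvement rating and no later score could remain.

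**Frequency.** One value in any of five on-treatment partial Mayo windows, or at discontinuation, is enough to escape the problem, and the protocol collects scores at discontinuation. This stands: f may be small.

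**Bias in Table 3.4.1.** A reader might infer that remission there is simply biased downward. The documents do not support that. The survey enrols moderate to severe active disease, so most baseline-only patients would be non-remitters, and counting them so is what NRI does. If patients without follow-up do worse, excluding them would bias remission upward. A factor linked to missing follow-up could be flagged under explicit NRI just as well. What remains is that the non-responder rule is undeclared and that baseline remitters escape it.

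**Conclusion.** The point holds as a defect in the written rule. Taken literally, 12.3, 12.4 and 12.6 make baseline the final value for an effectiveness-group patient with no later in-window value, and nothing visible in either document prevents it.

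The clear effects are:
- zero changes in the final rows of Tables 3.1.1 and 3.1.4, which shrink the mean change by the factor 1 - f;
- baseline CRP repeated in the final row of Table 3.5, which is descriptive only;
- baseline remitters counted as successes in Table 3.4.1, and baseline non-remitters handled by an unstated non-responder rule.

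No size can be derived, because neither f nor baseline remission in these patients is given. The percentages above are illustrations on assumed values.

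Two stronger readings should not be drawn. One is that the sponsor means to report pre-treatment values as outcomes; 13.3 suggests the opposite. The other is that up to 30% of patients are affected, which borrows a figure for a different quantity. The scope is also limited: Table 3.4, the other table labelled primary endpoint, and the fixed-visit rows, including Week 52, do not use the rule. The correction is worth making because it is cheap and removes a choice that the programmer would otherwise make.

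**What to change.** In SAP 12.3, 12.4 and 12.6, define the final assessment as the last value in a window after first administration: Week 4 onward for partial Mayo score and CRP, Week 24 onward for full Mayo score, or at discontinuation. Require the value to be dated after Day 1, so that a baseline score cannot re-enter through the discontinuation window of a patient who stopped after one dose. State also how values between windows, such as week 32, are treated.

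Patients without such a value have no final value in the Observed Case tables and Table 3.5. Report their number beside Table 3.4.1. Show 3.4.1 with them excluded and, as a sensitivity analysis, with them as non-remitters under the explicit NRI rule.

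The cost is a sentence or two in three sections, a program filter and one extra version of a table. The downsides are a smaller final-assessment denominator and possible upward bias in remission if patients without follow-up do worse. The NRI version addresses that bias.
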